15.3 Toxicity Monitoring

After the 20190312 protocol amendment, only the monitoring described below in the section entitled “Overall Adverse Event Monitoring” is applicable.

Initial Study Monitoring for Adverse Events: Once 6 subjects have been accrued to each arm of this study and the last patient has received the third vaccination and has been followed for approximately 2 weeks, toxicities up to that point will be formally monitored. A patient who does not complete this follow-up period without experiencing an unacceptable toxicity will be replaced for this initial monitoring of adverse events. If 1 or less of the 6 subjects within each arm experience an unacceptable toxicity, accrual will continue. Otherwise, if 2 or more of the 6 subjects within an arm experience unacceptable toxicity, the study will be carefully reviewed to determine if modifications to the protocol or treatment plan need to occur.

Study Drug Safety Arm Monitoring for Hypersensitivity Reactions (not applicable for patients enrolled on protocol version 6/12/18 or later): For the *study drug safety arm* (Section 11.4.3), unacceptable toxicity is defined as any hypersensitivity reaction within 6 hours after vaccine reaction that requires intervention to prevent life threatening symptoms, according to the PI and the study team. The PI will review the reaction to determine if it is unacceptable.

Corrective Action for Hypersensitivity Reactions in Study Drug Safety Arm (not applicable for patients enrolled on protocol version 6/12/18 or later): If 2 out of 3 Schedule A patients experience hypersensitivity reactions after Component A injection (Vaccine #1), the study will be put on hold in order to evaluate potential modifications to Component A to increase patient safety.

If 2 out of 3 Schedule A patients experiences hypersensitivity reactions after Component B injection (Vaccine #2), we will discontinue the use of Component B and continue all further vaccinations with Component A alone.

If 2 out of 3 Schedule B patients experience hypersensitivity reactions after Component B injection (Vaccine #1), but Schedule A patients have not experienced hypersensitivity reactions after Vaccine #1, we will discontinue the use of Component B in Schedule B patients and continue all further vaccinations with Component A alone.

If 2 out of 3 Schedule B patients experience hypersensitivity reactions after Component A injection during Vaccine #2, but Schedule A patients have not experienced hypersensitivity reactions after Vaccine #1, Schedule B patients will discontinue the use of Component B and continue all further vaccinations with Component A alone.

If 2 out of 3 patients from both Schedule A and B experience hypersensitivity reactions after Vaccine #1, the study will be put on hold and the study team will work on modifying the study drug to decrease the hypersensitivity reaction.

Overall Adverse Event Monitoring: The prevalence of unacceptable toxicities occurring during the initial 3 bi-weekly vaccinations administered concurrently with temozolamide will be monitored. If more than 25% of accrued patients experience unacceptable toxicities, then accrual will be suspended and reported toxicity will be carefully reviewed to determine

if accrual should be terminated or modifications to the protocol treatment should occur. This review will consider that patients will have different lengths of follow-up and duration of vaccination treatment.

As described in Section 11.5.3, the definition of unacceptable toxicity has been modified with v.20200117 of the protocol, and now excludes vaccine reactions indicative of immune response. Therefore, as of the time of this amendment, no patient had experienced an unacceptable toxicity under the new definition.

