11.5.4 Unacceptable Toxicities

The original definition of unacceptable toxicities in this study was any vaccine-related or any non-neurologic \geq Grade 3 toxicity of any duration not attributable to TMZ, bevacizumab, and/or disease progression; any Grade 4 toxicity, including neurologic events not due to progressive disease; or any life threatening-event not attributable to concomitant medication, co-morbid event, or disease progression. The definition of unacceptable toxicity was revised with v.20200117 of the protocol and will be defined now as any life-threatening \geq Grade 3 toxicity that is possibly, probably, or definitely related to the PEP-CMV vaccine with the following exceptions (updated in the v.20200504 protocol). A portion of the Grade 3 vaccine reactions noted in prior patient experiences with the PEP-CMV vaccine, described in Sections [11.5.1](#) and [14.2.1](#), will not be considered unacceptable if they are indicative of immune response. That is, toxicities such as Grade 3 flu-like symptoms, fever, and chills/rigors will not be considered unacceptable toxicities if the duration is less than 72 hours. Please see Section [11.5.1](#) for guidelines on management of immune response, including cytokine release syndrome (CRS). Any \geq Grade 3 organ toxicity (cardiac, renal, hepatic), including CRS-related toxicities such as hypotension and tachycardia, of any duration will be considered an unacceptable toxicity. Toxicities will be tracked on all subjects who received PEP-CMV vaccine using the NCI CTCAE (Version 4.03) criteria. Patients who experience unacceptable toxicities will not continue to receive vaccine therapy. Although not considered an unacceptable toxicity, any patient with \geq Grade 2 urticaria will not receive further vaccines, will be withdrawn from the study, and will be replaced if less than 3 vaccines have been administered without unacceptable toxicity.

The prevalence of unacceptable toxicities occurring during the initial 3 bi-weekly vaccinations or the vaccinations administered concurrently with temozolomide will be continuously monitored. If more than 25% of accrued patients experience unacceptable toxicities, then accrual will be suspended and reported toxicity will be carefully reviewed to determine if modifications to the protocol treatment should occur. Peptide vaccinations employing Montanide ISA-51 as adjuvants have generally been well tolerated in human patients in numerous phase I-III trials.

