15 STATISTICAL CONSIDERATIONS

15.1 Study Design and Conduct

A total of 70 patients may be consented on the main informed consent, in order to randomize a sufficient number of patients with newly diagnosed GBM who completed standard of care radiotherapy with temozolomide into one of two treatment arms. Patients will receive 3 bi-weekly (every other week) vaccinations during the first cycle of either: (Arm 1) 5-day standard of care temozolomide at 150-200 mg/m²/day, or (Arm 2) 21-day temozolomide at 75-100 mg/m²/day post chemo-radiation (please refer to study overview for timing of vaccine administration). We will target the treatment of 26 patients (13 per arm) who are evaluable for the primary immune endpoint. All patients will continue to receive PEP-CMV vaccine as described in the Treatment Plan at 4 (+2) week intervals for up to 20 vaccines, these vaccine administrations will coincide with TMZ cycles for those who are receiving TMZ.

With the 20190312 protocol amendment, the study's primary analysis has focused on patients who receive Component A only. Hence, we target the treatment of 26 patients (13 per arm) who received only Component A and are evaluable for the immune endpoints.

Once 6 subjects have been accrued to each arm of this study and the last patient has received the third vaccination and has been followed for approximately 2 weeks, toxicities up to that point will be formally monitored. Further accrual will be dependent upon the prevalence of unacceptable toxicity within each arm. See Section 15.4 for further details of monitoring guidelines.

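### The 25% toxicity rule has two counting windows: Section 15.3 counts vaccines 1 to 3 only, while the synopsis and Section 11.5.4 also count later vaccines given with TMZ

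*Combined protocol and SAP*

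**What the plan says.** Section 15.3 opens by saying that after the 20190312 amendment "only the monitoring described below in the section entitled" Overall Adverse Event Monitoring applies. That part reads: "The prevalence of unacceptable toxicities occurring during the initial 3 bi-weekly vaccinations administered concurrently with temozolamide will be monitored". Accrual is suspended once over 25% of accrued patients have had an unacceptable toxicity, and a review decides "if accrual should be terminated or modifications to the protocol treatment should occur". It adds: "This review will consider that patients will have different lengths of follow-up and duration of vaccination treatment".

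Section 11.5.4 and the synopsis give the same 25% threshold, but their window is "the initial 3 bi-weekly vaccinations or the vaccinations administered concurrently with temozolomide will be continuously monitored". On crossing the threshold, "then accrual will be suspended and reported toxicity will be carefully reviewed to determine if modifications to the protocol treatment should occur".

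Section 15.1 still describes a formal look once six patients per arm have been followed past vaccine 3, and says: "Further accrual will be dependent upon the prevalence of unacceptable toxicity within each arm". It sends the reader to Section 15.4 for the guidelines. The limits are in fact in Section 15.3, in the part that its opening sentence switches off.

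**The concern.** A suspension rule should give one answer for one set of data. Here the words that bring in later TMZ-concurrent vaccines stand in two current sections and are missing from the third, which is the statistical section. A team working from Section 15.3 would leave out events that a team working from Section 11.5.4 would count.

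Safety in combination with adjuvant TMZ is a primary objective (Section 8.2.1). Patients on 6 to 12 TMZ cycles receive most of their TMZ-concurrent vaccines after the third. For them, the choice of section decides whether those vaccines enter the rule at all.

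**Working it through.** **1. The wordings side by side**

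| Element | Section 15.3 | Synopsis and Section 11.5.4 |
|---|---|---|
| Window | Vaccines 1 to 3 | Vaccines 1 to 3, plus later vaccines given with TMZ |
| Frequency | Monitored | Continuously monitored |
| Threshold | More than 25% of accrued patients | Same |
| Review may lead to | Ending accrual or modifying treatment | Modifying treatment |

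Only the first row is a conflict. Continuous monitoring is a form of monitoring, and the shorter outcome list does not rule out ending accrual. In Section 15.3 the TMZ phrase only describes the initial three vaccines, so its stated window does not reach vaccine 4.

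Section 15.3 also cites Section 11.5.3 for the toxicity definition, which now stands in 11.5.4. This suggests, without proving it, that 15.3 was not kept in step.

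**2. Vaccines in dispute**

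Inputs:
- Vaccines 1 to 3 fall in TMZ cycle 1, which runs until two weeks after vaccine 3 (Section 11.1; Table 3, footnote 7).
- One vaccine is given in each later TMZ cycle (Section 11.1).
- MGMT-unmethylated patients enrolled after v20181218 have one cycle. Methylated or inconclusive patients, and all those enrolled earlier, are planned for 6 to 12.

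Assumption: concurrent means within a TMZ cycle. TMZ is taken on days 1–5 or 1–21 and vaccination is on about day 23, so a same-day reading would cover no vaccine.

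For c cycles, Section 15.3 counts 3 vaccines, Section 11.5.4 counts 3 + (c − 1), and the difference is c − 1.

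| TMZ cycles | 15.3 | 11.5.4 | In dispute |
|---|---|---|---|
| 1 | 3 | 3 | 0 |
| 6 | 3 | 8 | 5 |
| 12 | 3 | 14 | 11 |

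From vaccine 4 on, vaccine k falls in cycle k − 2, so vaccine 6 is in cycle 4.

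**3. Allowing for progression**

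These are maxima, because progression ends vaccination. Assume exponential PFS from vaccine 3, no other dropout, vaccines every 4 to 6 weeks, and a median PFS between the two values in Section 9.7 (6.7 and 29.2 months). With r = 2^(−interval/median), the expected number in dispute is the sum of r^j for j = 1 to c − 1.

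- Low end: 6 weeks = 42/30.44 = 1.38 months, so r = 2^(−1.38/6.7) = 0.867. The sums are 3.3 (6 cycles) and 5.2 (12 cycles).
- High end: 4 weeks = 0.92 months, so r = 2^(−0.92/29.2) = 0.9784. The sums are 4.7 and 9.7.

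**4. Effect on the decision**

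Let N be the number accrued, a the patients with an unacceptable toxicity in vaccines 1 to 3, and b those with one at a later TMZ-concurrent vaccine. The groups do not overlap, because Section 11.5.4 stops vaccination after an unacceptable toxicity. Section 15.3 computes a/N and Section 11.5.4 computes (a + b)/N. The decisions differ whenever a/N ≤ 0.25 < (a + b)/N.

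**5. How much the window can matter**

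The documents give no per-vaccine toxicity rate. Assume a constant, independent risk p per vaccine, with every counted vaccine given. A patient's chance of being counted is then 1 − (1 − p)^k.

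| p (assumed) | k = 3 | k = 8 | k = 14 |
|---|---|---|---|
| 1% | 3.0% | 7.7% | 13.1% |
| 2% | 5.9% | 14.9% | 24.6% |
| 5% | 14.3% | 33.7% | 51.2% |

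Progression would lower the last two columns.

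**The case against.** **The mismatch is small and may not bite.** It is one dropped phrase, and it makes no difference for single-cycle patients. The threshold sentence repeats no window, so a broad reading of Section 15.3 is possible, and Section 15.3 reports that "no patient had experienced an unacceptable toxicity under the new definition" as of v20200117. All of this stands and limits the severity. It does not settle which window governs. The sentence on unequal follow-up tells the review what to weigh once the rule has tripped, not which events trip it.

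**A reader might infer that vaccines given without TMZ go unmonitored.** Neither wording names them, and with 1, 6 or 12 cycles they are up to 17, 12 or 6 of the 20. But leaving them out of this rule fits the objective of safety in combination with adjuvant TMZ. Other oversight also covers them: patient-level stopping (11.5.4), the investigator's trend review (11.5.5), monitoring that can lead to study closure (14.3), annual committee review (17.5), and a final safety analysis of everyone vaccinated (15.4.1).

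**A reader might infer a gap once accrual closes.** The rule's first action is indeed to suspend accrual. However, the review may also modify treatment, and the oversight just listed continues. The DSMBplus charter is held separately, and the opening part of Section 11.5 was not available for this review, so a missing procedure cannot be asserted.

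**A reader might work out a trip count from the target of 26.** That is the wrong denominator. The rule uses accrued patients, whereas 26 is the number evaluable for immune response. Patients withdrawn before the post-vaccine 3 sample are replaced (11.10.3), and on 20200110 only 8 of 15 Component-A-only patients were evaluable (15.1), though some may have been pending.

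**Conclusion.** The point holds as an internal inconsistency in the one toxicity rule of Section 15.3 still in force. Its size is up to 5 vaccines per patient with 6 TMZ cycles and up to 11 with 12, or about 3.3 to 4.7 and 5.2 to 9.7 under the progression assumptions above. It is zero with one cycle. The dose counts rest on reading concurrent as within a TMZ cycle.

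The same data can give different suspension decisions, but how likely that is cannot be stated, because the documents give neither a late toxicity rate nor a final accrued number. The differences in monitoring frequency and review outcomes are compatible and need only tidying. Nothing here shows late harm or a general failure of safety oversight.

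**What to change.** - In Section 15.3, replace the window with that of Section 11.5.4: "the initial 3 bi-weekly vaccinations or the vaccinations administered concurrently with temozolomide will be continuously monitored".
- Give one list of review outcomes in Section 15.3, Section 11.5.4 and the synopsis, including the option to end accrual. Keep the Section 15.3 sentence on unequal follow-up.
- In Section 15.1, mark the six-per-arm look as superseded.

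The cost is a sentence or so in each of three places and a note in Section 15.1. No new data are needed, because Table 3 (footnote 22) already has adverse events collected throughout. The downside is that the count runs over longer and unequal exposure than Section 15.3 now states, so the review may trip more often if later events occur. Two of the three sections already require that exposure, and crossing 25% suspends accrual for review without automatically stopping vaccination.

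Extending the count to vaccines given without TMZ, or adding a procedure for after accrual closes, is optional. Widening the count to all 20 vaccines at an unchanged 25% would make a materially different rule, and the threshold would need to be reconsidered first.

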Following the safety events of vaccine reactions that were initially reported on 20170407, the study was amended to investigate, in a separate unrandomized drug safety cohort of 6 patients, the etiology of these events. Within this cohort, patients were consented to receive study vaccine with standard of care (SOC) 5-day TMZ at 150-200 mg/m²/d for 28-day cycles with various sequences of vaccine components A and B. Details of this safety assessment plan are provided in Section 11.4.3. Upon completion of this unrandomized portion of the study, the randomized study was allowed to reinitiate with changes to vaccine administration procedures based on observations made in the safety cohort (protocol v. 20180719). Subsequently, Component B was removed from the vaccine for future patients due to problems with availability and supply (protocol v.20181218). On 20190130, Component B was removed from the vaccine for all patients (current and future) due to two new safety events observed and reported in January 2019.

As of 20190312, 13 patients have been enrolled on the study:

Periods of Study Conduct	Patient Enrollment Description as of 20190312
Initial – Randomized	3 patients randomized and treated with 1-2 vaccinations that included Component A and B as originally planned before study suspension: 
• 2 patients assigned to standard TMZ on days 1-5• 1 patient assigned to dose-intensified TMZ on days 1-21
Safety Cohort (See Section 11.4.3)	6 patients treated with standard TMZ with different sequences of Component A and B
Resumed – Randomized	Once randomization resumed, the 1 st 4 patients randomized:

	
• 2 patients assigned to standard TMZ with vaccine that included Component B; Component B was dropped for these 2 patients due to safety events (one patient received only one vaccine containing Component B, and the other patient received 3 vaccines containing Component B).• 2 patients assigned to dose-intensified TMZ – Component B was dropped before these patients started treatment; hence, only Component A was part of vaccine. 
For all subsequent patients enrolled, the vaccine includes Component A only.

--	---

As of protocol version 20190312, the primary analysis of this study will focus on only those patients who receive Component A alone.

As of 20200110, 15 patients have received only Component A of which 8 are currently evaluable for the immune response primary endpoint.

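### The only numeric accrual-suspension rule pools the two TMZ arms, so it is nearly blind to excess toxicity in one arm, although Sections 15.1 and 15.4.1 treat toxicity by arm

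*Combined protocol and SAP*

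**What the plan says.** Section 15.3 opens by limiting what still applies: "After the 20190312 protocol amendment, only the monitoring described below in the section entitled" Overall Adverse Event Monitoring. That part contains one numeric rule: "If more than 25% of accrued patients experience unacceptable toxicities, then accrual will be suspended". The synopsis and Section 11.5.4 carry the same threshold. None of the three names an arm, a minimum number of patients, or the set of patients that forms the denominator. Suspension leads to a review, not to automatic closure.

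The check that 15.3 switches off was by arm: it called for review "if 2 or more of the 6 subjects within an arm experience unacceptable toxicity". Section 15.1, however, still describes that formal look and still makes further accrual depend on how common unacceptable toxicity is in each arm. Section 15.4.1 estimates the percentage with unacceptable toxicity separately by arm.

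On the count so far, 15.3 reports that, when v.20200117 changed the definition, "no patient had experienced an unacceptable toxicity under the new definition". Section 15.1 gives the numbers treated: "As of 20200110, 15 patients have received only Component A of which 8 are currently evaluable".

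**The concern.** TMZ schedule is the randomised factor, and safety of the vaccine with adjuvant TMZ is a primary objective. If one schedule makes vaccine reactions worse, the excess will sit in one arm. A pooled percentage roughly halves it, and a run of earlier patients without events dilutes it further. The protocol then says two things about accrual: 15.1 makes it depend on each arm, while 15.3 leaves in force only a rule that cannot tell the arms apart. The documents give no operating characteristics for that rule, so the reader cannot see how weak it is in the situation that matters most here. At stake is continued accrual to an arm whose toxicity is well above the sponsor's own threshold.

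**Working it through.** The 25% is a design constant, so there is no derived figure of the plan's to reproduce.

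**Inputs**
- Threshold: strictly more than 25% (15.3, 11.5.4, synopsis).
- Past Component A-only patients: 15, as of 20200110 (15.1).
- All vaccinated patients: 3 initial + 6 safety cohort + 2 resumed patients who received Component B + 15 = 26 (derived from 15.1).
- Past events: 0 (15.3, at v.20200117).
- Further patients: 26 − 8 = 18. This assumes that every new patient becomes evaluable and no more of the 15 do.
- True toxicity rates and the arm split of the 15 are not in the documents. They are assumptions below.

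**Fixed-count check at target size.** Six events in one arm and none in the other: 6/13 = 46% and 0/13 = 0%, but pooled 6/26 = 23.1%. No suspension.

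**Consecutive events needed.** With e past events in b past patients, (e + k)/(b + k) > 0.25 gives k > (b − 4e)/3.
- Pooled, 0/15: k > 5, so 6 (5/20 = 25.0% does not trip; 6/21 = 28.6% does).
- Pooled, 0/26: k > 8.67, so 9 (8/34 = 23.5%; 9/35 = 25.7%).
- Pooled, 1/15 or 2/15: k > 3.67 or k > 2.33, so 4 or 3.
- Within an arm, 0/7 or 0/8: k > 2.33 or k > 2.67, so 3 (3/10 = 30.0%; 3/11 = 27.3%).

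**Probability of ever tripping.** Let P_n(x) be the probability of x events after n patients with no trip so far. Then P_{n+1}(x) = P_n(x)(1 − p) + P_n(x − 1)p, and any mass with x/(n + 1) > 0.25 is removed and counted as a trip. The rule is checked after every patient.

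| Pooled rule, next 18 patients | from 0/15 | from 0/26 |
|---|---|---|
| 5% in one arm, 45% in the other | about 0.014 | about 0 |
| 30% in both | 0.09 | 0.003 |
| 40% in both | 0.33 | 0.04 |
| 50% in both | 0.65 | 0.17 |
| 60% in both | 0.89 | 0.45 |

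Sensitivity to the zero: with one or two past events in the 15, the 5%/45% figure rises to about 0.06 or 0.21.

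Sensitivity to the number still to come, from 0/15: at 40% the probability is 0.11, 0.33 and 0.73 over 11, 18 and 34 further patients; at 50% it is 0.29, 0.65 and 0.96. The 11 assumes all seven non-evaluable patients become evaluable (26 − 15). The 34 assumes a yield of 8/15 persists (18 ÷ 8/15 = 33.75).

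**Same 25% within each arm, no restart.** Assume the 15 split 7/8 with no events, and 9 more patients join each arm. The chance that either arm trips is 1 − (1 − a)(1 − b), where a and b are the arm probabilities.

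| True rates | a (7 past) | b (8 past) | either arm |
|---|---|---|---|
| 5% / 45% | 0.0008 | 0.4575 | 0.46 |
| 5% / 5% | 0.0008 | 0.0003 | 0.001 |
| 10% / 10% | 0.0074 | 0.0036 | 0.01 |
| 15% / 15% | 0.0273 | 0.0152 | 0.04 |
| 20% / 20% | 0.0668 | 0.0411 | 0.11 |

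If the arm with the 45% rate is the one with 7 past patients, detection is 0.54. On the same patients, a pooled figure above 25% requires at least one arm above 25%, so the by-arm rule never misses a case that the pooled rule would catch.

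**The case against.** The pooled rule is not the only protection. Patients with unacceptable toxicity stop vaccine (11.5.4). The PI monitors adverse events continuously and may close the study, with annual Safety Oversight Committee review (14.3). A DSMBplus exists (17.8), and its charter is not in the documents, so it may hold a trigger that we cannot see. The trial has also acted without reaching a threshold: it suspended after the first three patients reacted, and it dropped Component B for everyone after two events. All of this stands and lowers the severity. None of it supplies a numeric accrual trigger in the text available.

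Three stronger readings are tempting, and the documents do not support them.

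- A reader might infer that the rule is inert. It is not: from 0/15 it trips with probability 0.65 at a common rate of 50% and 0.89 at 60% over 18 patients.
- A reader might infer that five unacceptable toxicities in the next five patients would go unnoticed. That rests on 5/20 being exactly 25% and on the stated zero. The sixth event trips the rule. With one qualifying event among the 15, five of five gives 6/20 = 30%, and the rule trips at the fourth.
- A reader might infer that the January 2020 redefinition emptied the numerator and left a mismatched denominator. Section 15.3 reports that past patients were judged under the new definition, so at that date the two matched.

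Pooling is the plain reading of 15.3, not an explicit statement, and 15.1 points the other way. That is a reason to reconcile the two sections.

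**Conclusion.** The point stands as a should-fix. The live numeric rule is pooled, 15.1 contradicts it, and 15.4.1 analyses safety at a level the rule does not monitor. Its main weakness is a one-arm excess: about 0.014 from 0/15 and about 0 from 0/26 for 5% against 45% over 18 patients. Against a common excess it is slow: 0.33 and 0.65 from 0/15 at 40% and 50%, and 0.04 and 0.17 from 0/26.

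These probabilities rest on assumed true rates, 18 further patients and a past count of zero. The zero is the least secure of these. It dates from v.20200117. The definition in 11.5.4 was updated afterwards and now counts hypotension of Grade 3 or worse whatever its duration, and 14.2.1 reports Grade 3 hypotension in this study without giving the number of patients, the arm or the vaccine component. A non-zero count would make the pooled rule more sensitive, but it would still not separate the arms.

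**What to change.** 1. Reconcile 15.1 with 15.3. Keep the sponsor's 25% and apply it cumulatively within each TMZ arm as well as overall, among Component A-only patients, with no restart of the count and no wait for the post-vaccine-3 visit.
2. Restate the past event count, by arm, under the current 11.5.4 definition. Before doing so, reconcile that definition with the synopsis, because 11.5.4 limits it to life-threatening events and the synopsis does not.
3. Put one identical sentence, with its denominator and its vaccination window, in the synopsis, 11.5.4 and 15.3. The window now differs: 15.3 covers only the first three vaccinations, while the other two also cover later vaccinations given with TMZ.

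The cost is protocol wording, a by-arm running tally and a few more review pauses: 0.001, 0.01, 0.04 and 0.11 when both true rates are 5%, 10%, 15% and 20%, on the 7/8 split above.

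Restarting the count in each arm and waiting for six patients to reach the post-vaccine-3 visit would detect more (0.92 for 5%/45%), but I do not recommend it. It discards valid earlier data and pauses falsely with probability 0.50 when both rates are 15%. Toxicity itself could delay its start, because patients who stop vaccine may never reach that visit.
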